
Osteopenia is common in children with cerebral palsy (CP) due to poor bone growth and muscle disuse and the problem extends to their adulthood. These children and young adults with CP, especially those with moderate physical disabilities, are unable to perform the required amount of exercise to improve their bone health as their typically developing counterparts. It has been demonstrated that strong bones or good bone health are related to muscle contractions during normal movements and regular exercises. As a result, non-traumatic fractures and bone pain are common in individuals with moderate severity of CP. Whole body vibration therapy (WBVT) has been recently proven to improve bone health and muscle function in healthy adults and post-menopausal women. It has been postulated that the vibration can stimulate the muscle spindles and elicit consistent muscle contractions. This would be a great advantage to the individuals with physical disabilities, who have limited movements and control in their body and prevent them to perform regular exercises as the normal individuals. Among the research of the WBVT for children with CP, promising results have been shown on gross motor function, balance and muscle strength for children with mild disability. Among these published studies, the vibration protocols required the study participants to perform simple exercises on the vibration platform. Very limited studies have been conducted on children and young adults with moderate CP. At present, we do not know if the effect of WBVT on this population group would be similar to those with mild CP in terms of their gross motor function and balance, because the moderate group is greatly compromised in their mobility and extent of regular exercises when compared with the normal population and those with mild CP. In addition, we do not know if static standing on the vibration platform would have similar effects on the gross motor function as doing simple exercises on the vibration platform.
	

This pilot study aims to examine the effect of WBVT on children and young adults with moderate severity of CP. A convenience sample of 5 pre-puberty children aged between 6 to 14 years and 5 young adults aged between 18 to 40 years with moderate CP, i.e. Gross Motor Function Classification System, GMFCS level III or IV, will be recruited to systematically investigate the effects of WBVT on their functional abilities. Individuals with GMFCS level III mobilise with hand-held mobility devices such as crutches or walking frames. Individuals of levels IV have very limited functional mobility and are mostly limited to an indoor environment.
	

Inclusion criteria:
 
 1. Aged 6 to 14 years or 18 to 40 years 2. Have a diagnosis of cerebral palsy with GMFCS levels III or IV 3. Be able to stand for 3 minutes independently or with own hand support on rails 4. Be able to follow simple instructions 5. Be able to undertake clinical examination; and 6. Informed consent by the participant's parent/ guardian 	

Exclusion criteria:
 
 1. There is a history of fracture within 8 weeks of enrolment of the present study and acute thrombosis, muscle or tendon inflammation, renal stones, discopathy or arthritis as reported by their parent/ guardian. 2. Women during pregnancy 3. Metal implants in their spine or lower limbs 	

The children and young adults will receive the WBVT when standing still on a vibration platform of 20 Hertz and a peak-to-peak amplitude of 2 mm: sessions will be 18 minutes in length, 4 days per week for 4 weeks. Assessments will be performed at baseline and at completion of the intervention to examine the
	

functional abilities of these children and young adults. The vibration frequency, duration and amplitude will be progressively increased over 2 weeks to the maximum of 3 minutes of 20 Hz with a peak-to-peak amplitude of 2mm. The intervention regime is as follows:

Day	Vibration 1	Rest 1	Vibration 2	Rest 2	Vibration 3	Rest 3
1st	1 min; 12Hz, 1mm	3 min	1 min; 12Hz, 1mm	3 min	1 min; 15Hz, 1mm	3 min
2nd	1 min; 15Hz, 1mm	3 min	1 min; 15Hz, 1mm	3 min	2 min; 15Hz, 1mm	3 min
3rd	2 min; 15Hz, 1mm	3 min	3 min; 15Hz, 1mm	3 min	3 min; 15Hz, 1mm	3 min
4th	2 min; 18Hz, 1mm	3 min	2 min; 18Hz, 1mm	3 min	2 min; 18Hz, 1mm	3 min
5th	3 min; 20Hz, 1mm	3 min	3 min; 20Hz, 1mm	3 min	3 min; 20Hz, 1mm	3 min
6th	3 min; 20Hz, 1mm	3 min	3 min; 20Hz, 2mm	3 min	3 min; 20Hz, 2mm	3 min
>7th	3 min; 20Hz, 2mm	3 min	3 min; 20Hz, 2mm	3 min	3 min; 20Hz, 2mm	3 min

The outcome measures comprise:

1. Gross Motor Function Measure (GMFM-66) item set to assess the gross motor function of study participants. Raw scores will be reported.
2. 2-minute walk test (2MWT) to assess submaximal exercise capacity of the study participants by measuring the distance covered in 2 minutes using a distance-measuring trundle wheel.
3. A validated Chinese version of the Pediatric Evaluation of Disability Inventory (PEDI) to assess functional capacities in the domains of daily activities, mobility and social/cognitive function.
4. Timed up and go test to assess balance and functional mobility of the study participants
5. Parental/ participant questionnaire to record satisfaction or comments on the intervention regime by children/ young adults/ parents of the intervention group.
6. Visual analogue scale of 0 to 10, in which 0 means no discomfort and 10 as extreme discomfort to assess discomfort, if any, associated with the intervention as reported by the study participants and/or by their carers' proxy

Analysis of data/ statistics:

Results will be presented as means, standard deviations and standard errors of measurement. Due to the present small sample size, non-parametric analyses would be conducted. Wilcoxon Sign test will be used to compare the outcome measures before and after the intervention for outcome measures #1 to #4 mentioned above. The feedback from the participants and/or their parents would be summarized, if any.

Significance of present proposal:

If the WBVT is found to be effective in improving BMD and functional abilities at the conclusion of the present study, the participants in the control group would be offered the same intervention regime as the intervention group upon study completion. The outcomes of this pilot study will show if this intervention is beneficial for children and young adults with moderate CP with respect to their functional abilities, and if there may be any related practical issues of this intervention to this population group. The outcomes also provide preliminary evidence to clinicians if this intervention is effective to improve functional abilities of children and young adults with moderate severity of CP and provide preliminary data to calculate sample sizes for future studies.

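### Does the day-by-day vibration table contradict the stated regime of 20 Hz, 2 mm and 18-minute sessions?

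*Combined protocol and SAP*

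**What the plan says.** The intervention paragraph gives the regime in two ways before the table.

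- The summary sentence has participants stand still and specifies "a vibration platform of 20 Hertz and a peak-to-peak amplitude of 2 mm: sessions will be 18 minutes in length, 4 days per week", over four weeks. It does not mention rest periods or a build-up.
- A later sentence in the same section says: "The vibration frequency, duration and amplitude will be progressively increased over 2 weeks to the maximum of 3 minutes of 20 Hz", at a peak-to-peak amplitude of 2 mm. The table is then introduced as the regime.

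The table sets out three bouts and three 3-minute rests per session, with minutes, frequency and amplitude for each bout. It begins on day 1 at 12 Hz and 1 mm. It reaches 20 Hz on day 5 and 2 mm in two of the three bouts on day 6. The last row, labelled >7th, has 20 Hz and 2 mm in all three bouts.

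The sample is described as "A convenience sample of 5 pre-puberty children aged between 6 to 14 years and 5 young adults", with no control of dose between participants. Under the analysis heading, outcomes 1 to 4 are compared before and after the intervention with a Wilcoxon test.

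**The concern.** Taken alone, the summary sentence promises 18 minutes at 20 Hz and 2 mm in every session for 4 weeks. The table does not deliver that. Early sessions are shorter and gentler, no session has more than 9 minutes of vibration, and one step goes down in duration when the text says duration goes up. A reader who saw only the summary sentence could even take it to mean 18 minutes of vibration, twice the table's maximum.

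Two things would be at stake if the mismatch were real. Operators might deliver different exposures to a group that the background describes as prone to fractures without trauma. The pilot's before-after change might also be attributed to an exposure that was never scheduled. That would mislead the design of a later study, which the protocol names as one purpose of the work.

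**Working it through.** **Inputs.** Bout minutes, frequency and amplitude come from the regime table. Each session has three rests of 3 minutes, so 9 minutes of rest. The number of sessions is 4 days x 4 weeks = 16. The last row is read as day 7 onward, which is an assumption tested below.

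**The plan's own figure.** Session length at full settings = 3 x (3 min vibration + 3 min rest) = 18 minutes. This reproduces the stated 18 minutes, provided that the rest after the last bout is counted.

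**Session by session.** Session length = sum of the three bouts + 9.

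| Day | Vibration (min) | Session (min) | Vibration at 20 Hz and 2 mm (min) |
|---|---|---|---|
| 1 | 1+1+1 = 3 | 12 | 0 |
| 2 | 1+1+2 = 4 | 13 | 0 |
| 3 | 2+3+3 = 8 | 17 | 0 |
| 4 | 2+2+2 = 6 | 15 | 0 |
| 5 | 3+3+3 = 9 | 18 | 0 |
| 6 | 3+3+3 = 9 | 18 | 6 |
| 7 to 16, each | 3+3+3 = 9 | 18 | 9 |

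**Totals over 16 sessions.**

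- Vibration: 3 + 4 + 8 + 6 + 9 + 9 + 10 x 9 = 129 minutes. Sixteen sessions of 9 minutes would give 144, so 129/144 = 90%.
- Session time: 129 + 16 x 9 = 273 minutes, against 16 x 18 = 288, so 95%.
- At 20 Hz and 2 mm: 6 + 10 x 9 = 96 minutes. This is 96/144 = 67% of the maximum possible and 96/129 = 74% of the vibration scheduled.
- Dividing 96 by 288 gives 33%, but this is not a fair comparison because 288 includes rest. Full settings in every session would score only 144/288 = 50%.

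**Timing of the build-up.** Two weeks at 4 days per week is 8 sessions. The table reaches full settings in all bouts at session 7, within the stated period.

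**The day 3 to day 4 step.** Vibration falls by 8 - 6 = 2 minutes (25%) while frequency rises from 15 to 18 Hz. Counting cycles does not remove the drop: 8 x 60 x 15 = 7,200 on day 3 and 6 x 60 x 18 = 6,480 on day 4, a fall of 10%. Frequency and amplitude never decrease anywhere in the table.

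**The last row's label.** If >7th is taken literally, day 7 has no row and sessions 8 to 16 (nine sessions) are wholly at full settings. Time at 20 Hz and 2 mm is then at least 6 + 9 x 9 = 87 minutes, and 96 if day 7 matches the later sessions. The symbol may also be a PDF reading error, so it is not counted against the plan.

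**The case for a change.** The strongest case for a change has three parts, and each is factually correct. The unqualified 18 minutes is wrong for sessions 1 to 4. The summary sentence does not say that half of the 18 minutes is rest. The day 3 and day 4 rows contradict the statement that duration rises, and reading the summary sentence as a target does not explain that step. The intervention is the only thing this pilot varies, and no report of delivered exposure is described, so a publication could simply repeat the summary sentence. Clearer wording would cost almost nothing.

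What stands is the wording. The summary sentence, the build-up sentence and the day 3 and day 4 rows do not fully agree and must be reconciled. A deliberate trade of shorter bouts for higher frequency at day 4 is possible, but the protocol does not say so.

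The rest does not stand. The reading of 18 minutes of vibration requires ignoring the stated maximum of 3 minutes, the tabulated rests and the inclusion criterion, which asks for only 3 minutes of standing. An operator with the table has every bout specified and no choice to make. That the report will name the wrong exposure is a guess about a document not yet written. A per-participant exposure report might be useful, but it would be an addition and would not correct this inconsistency.

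**Conclusion.** The trial schedules what it says it tests: a disclosed build-up to 20 Hz and 2 mm, followed by sessions at that level. The summary sentence is a loosely worded target and the table is the schedule. The shortfall against full settings throughout, 96 of 144 minutes, is almost all the announced build-up.

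The residue is clerical. Four early sessions run 12 to 17 minutes instead of 18, and one unexplained step lowers vibration by 2 minutes out of 129 (1.6%). The investigators must reconcile those statements, and this review takes no view on which is right.

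Nothing in the statistics turns on it. Every participant has the same schedule, the comparison is before against after within participants, no dose-response analysis is planned, and the sample of 5 + 5 is one of convenience. Run from the table, the trial gives the same data and the same tests whether or not the summary sentence is tidied.

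This rests on two assumptions: that operators work from the table, and that its last row means day 7 onward. If the second fails, time at full settings lies between 87 and 96 minutes and the conclusion is unchanged.

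### Four unranked before-after tests, with no primary outcome, decision rule or comparator, cannot show whether the intervention is beneficial

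*Combined protocol and SAP*

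**What the plan says.** The outcome list has six unranked items. Under Analysis of data/ statistics, the first four (GMFM-66, 2-minute walk test, PEDI, timed up and go) are tested: "Wilcoxon Sign test will be used to compare the outcome measures before and after the intervention for outcome measures #1 to #4 mentioned above". The PEDI item covers function "in the domains of daily activities, mobility and social/cognitive function", so it may yield three tests rather than one. The plan gives no primary outcome, significance level, sidedness, adjustment, or rule linking results to a conclusion. It also does not say whether the 5 children and 5 young adults are analysed together.

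The design text describes treated participants only: "The children and young adults will receive the WBVT when standing still on a vibration platform". On timing it says: "Assessments will be performed at baseline and at completion of the intervention".

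Under Significance of present proposal, the plan states: "The outcomes of this pilot study will show if this intervention is beneficial for children and young adults with moderate CP". The sentence after it is more modest: "The outcomes also provide preliminary evidence to clinicians if this intervention is effective to improve functional abilities", and the study is to "provide preliminary data to calculate sample sizes for future studies". The same section says that, if the therapy is found effective on BMD and function, "the participants in the control group would be offered the same intervention regime".

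**The concern.** Two separate gaps lie between the analysis and the promise to show benefit.

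The first is selection. With several unranked tests and no rule, the result used to support a benefit statement can be chosen after the data are seen. The chance that at least one test shows a false improvement is then generally higher than for a single test named in advance.

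The second is attribution. A before-after test asks whether scores changed, not why. Practice on the tests, maturation (particularly in children) and regression to the mean can all produce a change, and nothing in the analysis separates them from the intervention. Naming a primary outcome would close the first gap but not the second.

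At stake is what clinicians, a stated audience of the pilot, will take from it. The offer of the regime to a control group also depends on a finding of effectiveness that the plan never defines.

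**Working it through.** The plan states no error rate, power or sample-size calculation, so there is no figure of its own to reproduce.

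**Inputs from the documents:** 5 children and 5 young adults; four tested outcomes; three PEDI domains, hence 3 + 3 = 6 tests if each domain is tested.

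**Assumptions, none of them stated:** two-sided 0.05; exact tests; no true change; equally correlated, normally distributed changes. *False improvement* means a significant result in the favourable direction.

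**One test, 10 pooled pairs.** For the exact signed-rank test, two-sided p ≤ 0.05 requires a rank sum of 8 or less. Of the 2^10 = 1024 sign patterns, 25 qualify in each direction: 25/1024 = 2.44%.

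**Four tests.** If independent, 1 − (1 − 0.0244)^4 = 9.4%. By simulation with correlated outcomes: 8.0% at correlation 0.5, 6.8% at 0.7, 5.0% at 0.9.

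**Six tests.** If independent, 1 − (1 − 0.0244)^6 = 13.8%. By simulation: 10.8% at 0.5, 8.7% at 0.7, 6.0% at 0.9.

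**Plain sign test.** The test name in the plan could also mean this. The tail is (1 + 10)/1024 = 1.07% for one test. Four independent tests give 1 − (1 − 0.0107)^4 = 4.2%; simulation gives 2.8% at correlation 0.9.

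**Fewer walking pairs.** Eligibility admits GMFCS level IV and requires standing for 3 minutes, not walking. Two of the four tests need walking. If only 5 participants have usable pairs on both (an assumption), neither of these tests can reach 0.05, as the next calculation shows. Only the other two tests remain: 1 − (1 − 0.0244)^2 = 4.8% if independent, 4.2% at correlation 0.7.

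**Age groups tested separately, 5 pairs each.** The smallest exact two-sided p is 2/2^5 = 2/32 = 0.0625. No test can reach 0.05, so the rate is 0%. For the same reason an exact signed-rank interval from 5 pairs covers at most 1 − 0.0625 = 93.75%.

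| Reading | At least one false improvement |
|---|---|
| One signed-rank test, 10 pairs | 2.4% |
| Four tests, correlation 0 to 0.7 | 9.4% to 6.8% |
| Six tests, correlation 0 to 0.7 | 13.8% to 8.7% |
| Four tests, 5 pairs on both walking tests, correlation 0 to 0.7 | 4.8% to 4.2% |
| Four plain sign tests, correlation 0 to 0.9 | 4.2% to 2.8% |
| Age groups tested separately, exact | 0% |

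**Attribution.** As an illustration only, suppose a mean gain of 0.25 SD arises wholly from causes other than the intervention. A single signed-rank test on 10 pairs would then show improvement in about 10% of trials (simulation). The 0.25 SD has no basis in the documents. It shows only that limiting the number of tests does not address attribution.

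**The case against.** The strongest reply is that this is a pilot with a convenience sample of 10. The plan itself promises "The outcomes also provide preliminary evidence to clinicians if this intervention is effective to improve functional abilities" and data to "provide preliminary data to calculate sample sizes for future studies", and it commits in advance to testing all four outcomes. On this view, what remains is one overconfident sentence. Much of that stands. Strict familywise control is not needed here, and the point is modest in weight.

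The objection is also right about the numbers. The 7% to 9% is one scenario; alpha, pooling, exactness, the type of test, the correlation and the number of usable pairs are all assumed. A reader might infer that the plan has an established false-positive rate of that size. The documents do not support that, because equally admissible readings give anything from 0% to about 14%.

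A reader might also infer an intention to report only favourable results. Nothing in the text indicates this; the plan merely leaves the choice open.

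Finally, it can be said that multiplicity and the missing comparator are different problems. They are, but both bear on the same sentence, and curing only one would leave that sentence unsupported. The pilot label does not rescue it either, since the benefit wording stands in the current text beside the modest wording.

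**Conclusion.** The concern holds as a mismatch between analysis and stated conclusion. It does not depend on any particular error rate: with no primary outcome, no decision rule and no between-group comparison, the planned tests cannot show whether the intervention is beneficial.

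The size of the multiplicity part is conditional. It is about 7% to 9% against 2.4% for one test, given 10 pooled pairs, exact two-sided 0.05 signed-rank tests and correlation 0 to 0.7; other readings are lower or higher as tabulated. The attribution part holds under every reading.

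The mention of a control group might suggest that a controlled comparison exists. The design and analysis text describes no control arm and no between-group test, so that inference is not supported.

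In weight this lies between a minor point and one the sponsor should act on, because the plan already calls its evidence preliminary and the remedy is cheap.

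**What to change.** Three wording changes:

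1. **Analysis of data/ statistics.** Add: *The before-after tests of outcomes 1 to 4, including each PEDI domain, are exploratory and unadjusted. All will be reported whatever the result, each with the number of pairs, the median change and an interval at its attainable exact level (at most 93.75% with 5 pairs), beside the planned means and SDs. No single significant result will be used to claim benefit.* As an option, the sponsor may instead name one primary outcome before recruitment, tested once, and state whether the age groups are pooled. The choice is the sponsor's.
2. **Significance of present proposal.** Replace the promise to show benefit with: *will give preliminary estimates of before-after change in functional abilities; a before-after comparison alone cannot attribute this change to the intervention.* This is needed under either option in item 1.
3. **Same section.** Reconcile the sentence on effectiveness for BMD and on a control group with the rest of the plan, which describes no control arm and no BMD outcome.

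The cost is wording only: no extra participants, visits or assessments. The downside is that, with all tests labelled exploratory, no outcome can be claimed as significant on its own, and the pilot's stated promise becomes more modest.
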